## 1.0 BACKGROUND AND HYPOTHESES

Cystic fibrosis (CF) is a genetic disorder characterized by a chronic cycle of airway infection, obstruction, and inflammation leading to progressive loss of lung function and eventual respiratory failure. Nontuberculous mycobacteria (NTM) are increasingly being isolated from the sputum of individuals with CF with estimates of prevalence increasing from 1.3 percent in 1984 to 12 percent in 2012 [1]. The prevalence of NTM increases with age from 10% in children aged 10 years, to over 30% in adults over the age of 40 years [1]. NTM can cause progressive inflammatory lung damage, a condition termed 'NTM pulmonary disease' (NTM-PD). In particular, recent epidemiological studies have demonstrated that the presence of mycobacterium abscessus complex (MABSC) in the airways of patients with CF is associated with more rapid lung function decline and a higher mortality [1]. Patients with CF are predisposed to NTM-PD due to reduced CFTR mediated reactive oxygen species generation within macrophages leading to reduced intracellular killing [2]. Management of these patients includes an intensive phase with oral azithromycin and several intravenous antibiotics (e.g. amikacin, tigecycline, imipenem) for 3-12 weeks followed by a prolonged continuation phase with oral (e.g. azithromycin, moxifloxacin, minocycline, clofazamine), and inhaled amikacin. A significant barrier to effective treatment is the limited number of safe and effective antibiotics for treatment of MABSC-PD. While macrolides have been the mainstay of treatment for many years, their efficacy is limited by reduced susceptibility. In addition, the risk for acute kidney injury and/or hearing loss is significant in patients with CF with prolonged use of amikacin. Tigecycline demonstrates good in vitro activity and is one of the primary antibiotics during the intensive phase of treatment; however, this agent is associated with significant nausea and vomiting and is only available for intravenous administration. Results of a pharmacodynamic study in a hollow fiber model determined the a dose of 100mg twice daily was needed to achieve the optimal target attainment (>90% stasis); however, this dose was estimated to cause nausea/vomiting in nearly 100% of patients [3]. Omadacycline offers a significant advancement in the management of infections involving MABSC in CF due to its excellent activity [4-6], penetration into pulmonary secretions, improved tolerability, and good oral bioavailability [7-10].

The pharmacokinetics of a number of medications have shown to be altered in patients with CF [11,12]. In general, patients with CF demonstrate an increased volume of distribution when expressed in L/Kg of body weight, and increased total body clearance. In addition, the oral bioavailability of lipophilic medications is reduced due to pancreatic insufficiency. To our knowledge no study has evaluated the pharmacokinetics of omadacycline in patients with CF. The proposed study is designed to characterize the pharmacokinetics of intravenous and oral omadacycline in patients with CF and determine the optimal dosing regimen in preparation for future efficacy and safety studies in CF patients with MABSC lung infections.

The pharmacokinetics of omadacycline in healthy volunteers, special populations, and patients with complicated skin and skin structure infections has been well described [7-9]. The oral absorption is relatively rapid and the bioavailability is good. Of note is the reduced bioavailability observed with high-fat meals or in conjunction with dairy products; based on these observations omadacycline is recommended to be given under fasting conditions with no food or dairy/antacids/multivitamins for 2 and 4 hours after administration respectively [10]. Elimination of omadacycline occurs predominately through fecal excretion [10]. No dosage adjustment is necessary for renal or hepatic disease [10].

Of particular importance to the proposed study is the excellent pulmonary penetration of omadacycline noted in healthy volunteers [9]. Bronchoalveolar lavage studies performed at

steady-state following omadacycline 100mg IV daily revealed epithelial lining fluid and alveolar macrophage exposures 2-fold and 30-fold higher respectively, than free drug exposures in plasma. These exposures also exceeded that of tigecycline indicating greater pulmonary penetration with omadacycline.

Our study hypothesis is that omadacycline will exhibit good oral bioavailability in patients with CF.

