## 2.0 OBJECTIVES AND PURPOSE

### Primary Objective:

Determine the concentrations of omadacycline in plasma of patients with CF following single dose IV and PO administration.

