### 10.2 Endpoint Definitions

PK parameters of omadacycline including the area under the curve, maximum concentration and time to maximum concentration in patients with CF.

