## 13.0 DATA/STATISTICAL CONSIDERATIONS

### 13.1 Pharmacokinetic analysis

Pharmacokinetics will be performed using standard noncompartmental methods.

The maximum concentration and time to maximum concentration will be from the

observed data. The area under the curve will be calculated using the trapezoidal rule. Absolute bioavailability will be determined by a ratio of the  $AUC_{PO}/AUC_{IV}$ .

In addition, population pharmacokinetic analysis will be performed using the maximum likelihood estimation via the EM algorithm with sampling (MLEM) as implemented in ADAPT 5 (Biomedical Simulations Resource, University of Southern California). Multiple candidate models will be evaluated to identify the model that best describes the observed plasma concentration data.

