## 13.2 Statistical Analysis

Twelve patients with CF will participate in this study. The endpoints for this study are descriptive in nature and the sample size is similar to other studies with these endpoints.

Patient demographics, clinical characteristics, and pharmacokinetic parameters will be summarized using descriptive statistics.

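### The only hypothesis is 'good' oral bioavailability, but F is not a named endpoint, has no interval or reference value, and its formula omits the 300 mg versus 100 mg dose difference

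*Combined protocol and SAP*

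**What the plan says.** All places are in the combined protocol and SAP.

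- **Section 1.0** gives the only hypothesis: "Our study hypothesis is that omadacycline will exhibit good oral bioavailability in patients with CF". For people without CF it says only that "The oral absorption is relatively rapid and the bioavailability is good", with no figure. It also gives a reason why CF might differ: "the oral bioavailability of lipophilic medications is reduced due to pancreatic insufficiency".
- **Section 2.0**, primary objective: "Determine the concentrations of omadacycline in plasma of patients with CF following single dose IV and PO administration". Bioavailability is not mentioned.
- **Section 3.0** has each of 12 patients receive 100 mg IV and, after a 1-week washout, 300 mg orally.
- **Section 10.2** defines the endpoints as "PK parameters of omadacycline including the area under the curve, maximum concentration and time to maximum concentration in patients with CF".
- **Section 13.1** says "Absolute bioavailability will be determined by a ratio of the" oral to the IV AUC, written AUC_PO/AUC_IV. No dose appears in the expression.
- **Section 13.2** says "The endpoints for this study are descriptive in nature and the sample size is similar to other studies with these endpoints", and plans descriptive summaries of the pharmacokinetic parameters.

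**The concern.** The quantity in the hypothesis is the least specified quantity in the plan. F is calculated, but it is not named as an endpoint, no interval is attached to it, and nothing says what value or comparison would count as good. Whether the hypothesis was supported would be decided after the estimate is seen, with no statement of how far an estimate from 12 patients may lie from the truth.

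This matters because section 1.0 itself raises the possibility of reduced absorption in CF and says the results will inform dosing in later studies.

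The formula adds a plain error of definition. Absolute bioavailability compares exposure per unit of dose. The oral dose here is three times the IV dose, so the ratio as printed is not F. A reader who applies section 13.1 as written and one who normalises for dose would report figures that differ threefold from the same data.

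**Working it through.** **1. The stated sample size.** N = 12 rests on similarity to other studies. No SD, target precision, alpha or power is given, so there is no calculation to reproduce.

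**2. The dose term.** Inputs: 300 mg oral and 100 mg IV (sections 3.0 and 7.1), and the ratio in section 13.1. If clearance is the same in both periods, AUC_IV = 100/CL and AUC_PO = F × 300/CL. The printed ratio is therefore

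AUC_PO/AUC_IV = (F × 300)/100 = 3F.

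| True F (illustrative) | Ratio as printed | (AUC_PO/300)/(AUC_IV/100) |
|---|---|---|
| 0.20 | 0.60 | 0.20 |
| 1/3 | 1.00 | 1/3 |
| 0.50 | 1.50 | 0.50 |
| 0.70 | 2.10 | 0.70 |

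Above F = 1/3 the printed ratio exceeds 1 and would draw attention. At or below 1/3 it looks like a plausible bioavailability and would not. The documents give no value of F, so these rows are illustrations.

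**3. Precision with 12 pairs.** Let SD be the between-patient standard deviation of each patient's log ratio, ln F. The documents give no figure, so 0.2 to 0.5 is assumed. The 95% interval for the geometric mean is the estimate multiplied and divided by

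exp(t × SD/√12), with t(0.975, 11 df) = 2.201.

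| Assumed SD | t × SD/√12 | Factor | Interval if the estimate is 1/3 |
|---|---|---|---|
| 0.2 | 0.127 | 1.14 | 0.29 to 0.38 |
| 0.3 | 0.191 | 1.21 | 0.28 to 0.40 |
| 0.4 | 0.254 | 1.29 | 0.26 to 0.43 |
| 0.5 | 0.318 | 1.37 | 0.24 to 0.46 |

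The upper end depends on the assumption. If one starts instead from a within-patient CV of AUC of 15% to 50%, so that SD = √2 × √ln(1 + CV²), the factor runs from 1.14 to 1.53.

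**4. Does the AUC method disturb F?** Section 11.0 uses the same sampling times, to 72 hours, for both routes. In a one-compartment model with assumed half-lives of 12, 16 and 24 hours and assumed absorption rates of 0.5 to 2 per hour, the linear trapezoidal rule stopped at 72 hours on both routes changes F by about 0.1% to 1.2%. Errors in the two AUCs largely cancel, provided that both are taken on the same basis.

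**5. What a pass/fail rule would do.** Suppose the lower 95% limit had to exceed 80% of a reference value (assumed) and the true F equalled that reference. With 12 patients the rule is met with probability 94%, 65%, 42% and 29% for SD 0.2, 0.3, 0.4 and 0.5.

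**The case against.** The strongest reply is that this is an openly descriptive study of 12 patients. F is a planned analysis, the endpoint list is introduced by a word that leaves it open, and any pharmacokineticist would normalise for dose without being told. Much of that stands. F is left unnamed in section 10.2, not left unanalysed, and a descriptive study needs no formal test. The dose omission may well be put right in practice, but the written formula is still wrong, and a low F would not expose it.

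A reader might infer more than the documents support:

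- **That no result could contradict the hypothesis.** A very low F plainly could. What is missing is a reference set in advance.
- **That the analysis ignores pairing, uses an arithmetic mean, applies the linear rule or stops at the last sample.** The plan states none of these. It refers to standard noncompartmental methods, and the sentence "The area under the curve will be calculated using the trapezoidal rule" specifies neither the linear form nor truncation. Step 4 shows that truncation and the linear rule would hardly move F. A bias from oral profiles ending earlier than IV profiles has no support in the text.
- **That clearance and volume will go unestimated.** Section 13.1 also plans a population model, which ordinarily yields both.
- **That the hypothesis needs a pass/fail benchmark.** Step 5 shows that such a rule would often fail a true hypothesis at this sample size.

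**Conclusion.** The point holds in a limited form. The plan's only hypothesis concerns F, yet F is not named in section 10.2, has no interval and has no reference value, and the formula in section 13.1 returns 3 × F at the stated doses. The factor of three is arithmetic and needs only the usual assumption of equal clearance in the two periods. The precision figure, a factor of 1.14 to 1.37 either way, rests on an assumed log-ratio SD of 0.2 to 0.5 and on all 12 patients completing both periods. Nothing here calls for a change to the design, sampling or sample size. It is a correction of definition and reporting that should be made before analysis, and the reference value or rewording should be settled before the first dose.

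**What to change.** 1. **Section 13.1:** define F for each patient as (AUC_PO/300)/(AUC_IV/100), and state that AUC is taken on the same basis for both routes.
2. **Section 13.2:** report the geometric mean F with a 95% t-interval calculated on the log scale.
3. **Section 10.2:** name F among the endpoints.
4. **Section 1.0:** either state, before the first dose, the reference value against which the estimate and its interval will be read, or reword the hypothesis as an aim to estimate F in CF.
5. **Sample size statement in 13.2:** add the expected precision for 12 patients (95% interval = estimate multiplied and divided by 1.14 to 1.37 for a log-ratio SD of 0.2 to 0.5), with the SD labelled as an assumption.

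The cost is a few lines of text and analysis, with no new patients, samples or procedures. The downside is that the interval will show openly how limited the precision of 12 patients is.

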## 2.0 OBJECTIVES AND PURPOSE

### Primary Objective:

Determine the concentrations of omadacycline in plasma of patients with CF following single dose IV and PO administration.

## 3.0 STUDY DESIGN

This study will be conducted using a prospective single dose, single-arm design to characterize the pharmacokinetics of omadacycline intravenous/oral (IV/PO) in CF. A total of 12 adult patients with CF will participate in the study and will receive a single dose of omadacycline 100mg IV followed by a 1-week washout and receipt of 300 mg PO.

## 4.0 DRUG/DEVICE INFORMATION

4.1 Omadacycline (Nuzyra) is a tetracycline class antibacterial indicated for the treatment of adult patients with the following infections caused by susceptible microorganisms:

Community-acquired bacterial pneumonia (CABP)

Acute bacterial skin and skin structure infections (ABSSSI)

The recommended dosage of omadacycline is 300 mg administered once daily orally (tablet) or as an intravenous infusion (IV) of 100 mg over 0.5 hour for 7-14 days.

## 5.0 SELECTION AND WITHDRAWAL OF SUBJECTS

### 5.1 Inclusion Criteria:

- Diagnosis of CF based on positive sweat chloride or known CF mutation
- Age  $\geq$  18 years

### 5.2 Exclusion Criteria

- Presence of an ongoing acute pulmonary exacerbation defined based on clinical signs & symptoms and an acute decline in relative FEV1 of 10% or greater.
- Pregnancy or breastfeeding
- Serious past allergy to a tetracycline antibiotic

- No alcohol, nicotine, or caffeine-containing products during the study period
- Hemoglobin < 8 g/dL

### 5.3 Withdrawal Criteria

Subject can be discontinued from the study for any of the following reasons:

- Subject's personal reasons
- Allergic reaction to the medication
- Other significant study related adverse events

## 6.0 STRATIFICATION/DESCRIPTIVE FACTORS/RANDOMIZATION SCHEME

6.1 Stratification factors: Not applicable.

6.2 Descriptive factors: Not applicable.

6.3 Randomization: Not applicable.

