## 7.0 STUDY AGENT ADMINISTRATION OR INTERVENTION AND TOXICITY MANAGEMENT PLAN

7.1 You will receive omadacycline administered in doses of 100 mg intravenously over 0.5 hour followed by a 1-week washout and receipt of 300 mg PO.

AGENT	DOSE	ROUTE	DAYS	ReRx	NOTES
Omadacycline	100 mg	I.V. over 0.5 hours	1	Once	
Omadacycline	300 mg	PO	1	Once	-Fast for at least 4hours and then take omadacycline tablet with water. -After oral dosing, no food or drink (except water) is to be consumed for 2 hours and no dairy products, antacids, or multivitamins for 4 hours.

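### Every patient receives IV first and oral second, so a period effect cannot be separated from oral bioavailability; randomising the order would remove this risk at small cost.

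*Combined protocol and SAP*

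**What the plan says.** Section 3.0 describes a "prospective single dose, single-arm design to characterize the pharmacokinetics of omadacycline intravenous/oral (IV/PO) in CF" and fixes the sequence: each patient "will receive a single dose of omadacycline 100mg IV followed by a 1-week washout and receipt of 300 mg PO". Section 7.1 repeats the order ("followed by a 1-week washout and receipt of 300 mg PO"). Section 6 adds "6.3 Randomization: Not applicable". None of these sections explains why IV comes first.

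Section 13.1 defines the quantity affected: "Absolute bioavailability will be determined by a ratio of the" oral AUC to IV AUC. The one hypothesis, at the end of section 1.0, is that oral bioavailability in CF will be good; no cut-off defines good.

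On analysis, section 13.2 says "Twelve patients with CF will participate in this study" and "The endpoints for this study are descriptive in nature and the sample size is similar to other studies with these endpoints". It plans descriptive summaries only, with no interval for F, no period term and no statement that a period effect is assumed absent. Section 11.0 gives both doses the same sampling schedule, from predose to 72 hours.

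**The concern.** When every patient takes the routes in the same order, the oral-to-IV comparison is also a week-2-to-week-1 comparison. A change that moves patients in a common direction between the weeks is read as bioavailability, and nothing in the data can show that it happened.

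The plan leaves some room for such a change. Background CF medication may continue (section 7.3), with no rule that it be held constant between doses. An ongoing exacerbation is an exclusion criterion (section 5.2), but no recheck before the oral dose is described.

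What is at stake is the within-patient ratio and the hypothesis that rests on it. The primary objective (concentrations after each route) and the endpoints in section 10.2 need no contrast between routes. The design already has two periods, a washout and matching sampling, so the order could be randomised without more patients or visits.

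**Working it through.** **Inputs from the documents.** n = 12, each patient receiving both routes (3.0, 13.2); IV 100 mg always first, oral 300 mg second, one week (168 h) apart (3.0, 7.1); F from the AUC ratio (13.1). The sample size of 12 rests on no alpha, power, SD or precision target, so there is no plan figure to reproduce.

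**Assumptions.** The documents give no within-patient CV, period effect or half-life. All values of these below are assumed. F means the dose-normalised ratio; a period effect multiplies it in the same way with or without normalisation.

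**1. Aliasing.** Write log AUC = patient + route + period + error. With fixed order, the mean of (log AUC oral − log AUC IV) estimates log F + (period 2 − period 1). The estimated ratio is therefore F times the period ratio: a period ratio of 1.10 gives an estimate 10% too high, and 0.90 one 10% too low.

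**2. Size relative to sampling error (illustration).** SD of the log ratio = sqrt(2 × ln(1 + CV²)); SE = SD/sqrt(12), with 11 degrees of freedom. At CV 20%, SE = 0.0809. Coverage of a nominal 90% paired interval follows from the noncentral t distribution with shift ln(period ratio)/SE; at +10% the shift is 0.0953/0.0809 = 1.18.

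| Assumed period effect | Coverage, CV 20% | Coverage, CV 30% |
|---|---|---|
| +5% | 85% | 87.5% |
| +10% | 70% | 81% |
| +15% | 51% | 71% |

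**3. Randomised order, 6 + 6.** Log F is estimated by half the difference between the sequence means of (period 2 − period 1). An additive period effect on the log scale cancels. SE = (SD/2) × sqrt(1/6 + 1/6) = SD/sqrt(12), the same as before. Degrees of freedom fall from 11 to 10, so the 90% multiplier rises from 1.796 to 1.812 (0.9%). At CV 20% the interval factor goes from 1.156 to 1.158. In simulation at CV 20%, with period ratios from 0.80 to 1.20, coverage stayed at about 90%.

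**4. Carryover.** Taking simple exponential decline, the fraction of exposure left after 168 h is r = 0.5^(168/half-life). The oral dose delivers 3F times the IV exposure (300F/100). Oral drug carried into a later IV period is then 3F × r of the IV AUC; IV drug carried into a later oral period is r/(3F) of the oral AUC.

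| Assumed half-life | r | Oral into IV, F = 1/3 | Oral into IV, F = 1 | IV into oral, F = 1/3 | IV into oral, F = 1 |
|---|---|---|---|---|---|
| 24 h | 0.8% | 0.8% | 2.3% | 0.8% | 0.3% |
| 48 h | 8.8% | 8.8% | 26.5% | 8.8% | 2.9% |

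The 6 + 6 estimate is multiplied by sqrt((1 + r/(3F))/(1 + 3Fr)). At 48 h and F = 1 this is sqrt(1.029/1.265) = 0.90, about 10% low, against about 3% high under the fixed order. At 24 h and F = 1 it is sqrt(1.0026/1.0234) = 0.99, about 1% low. At F = 1/3 the two carryovers cancel in the 6 + 6 design, while the fixed order is high by r.

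**The case against.** The best defence is that this is a 12-patient descriptive study. Section 13.2 plans no interval or test for F, and a hypothesis without a cut-off has no boundary for a 5% or 10% shift to cross. That stands. It makes the coverage figures illustrative and limits the weight of the point, but the point estimate of F is shifted however it is summarised.

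A reader might infer from the fixed order that F will be biased. The documents do not support that. They show no period effect, and a period effect must move patients in a common direction; individual week-to-week changes are ordinary within-patient variation. Lapses in the oral fasting and dairy rules (7.1) belong to the route, and randomising the order would not remove them. Nothing suggests that samples are handled differently in the two weeks.

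Nor does the small sample make matters worse. For a given bias, coverage falls as n grows, and a 5% effect costs only a few points here.

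A reader might also infer that randomising disposes of every order problem. It removes an additive period effect, not unequal carryover, and if F exceeds 1/3 the oral-first sequence has the larger carryover. Against that, the plan itself relies on a one-week washout and takes a predose sample that would reveal residual drug.

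The population model in 13.1 helps only in part: a clearance change between weeks may show in the terminal slope, but otherwise F absorbs the period difference. Finally, the entry under 6.3 is consistent with a single-arm design and is not itself an error.

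**Conclusion.** The point holds as a design risk of moderate weight. Route and period are exactly aliased, no reason is given for the order, and the ratio affected bears on the only stated hypothesis. The bias in F would equal the period effect, whose size the documents do not give.

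Randomising the order removes an additive log-scale period effect with the same patients, doses, washout and sampling, for about 1% more interval width on the log scale. This statistical cost is calculated; that the operational cost is also small is an inference, since the documents give no scheduling information. The advantage further depends on carryover being small. That is so for assumed half-lives up to 24 h (residual oral exposure at most 0.8% to 2.3% of the IV AUC for F from 1/3 to 1) but not assured at 48 h (8.8% to 26.5%).

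**What to change.** Change 3.0, 6.3 and 7.1 to a randomised two-sequence order: 6 patients IV then oral, 6 oral then IV, with doses, washout and sampling unchanged. In 13.1 or 13.2, estimate F from log AUC with patient, period and route in the model. Report period-2 predose concentrations in both sequences, so that carryover can be seen.

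The cost is a 12-line randomisation list, short wording changes to the protocol and consent form, one degree of freedom, slightly more complex scheduling, and a small carryover risk in the oral-first sequence.

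If there is a reason to give IV first, state it and keep the order. Section 13.2 should then say that F assumes no period effect, and the report should give period-2 predose concentrations and any change in background medication between the doses.
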